
## 2. PRIMARY AIMS AND LONG-TERM GOAL

As a first step to collect preliminary data on the potential mechanisms of action of RLIC in humans, we will perform a small multicenter randomized pilot clinical trial of 10 subjects with ICAS at 4 participating sites (MUSC, MCG, UCLA and the University of Southern California (USC)) to accomplish the following **primary aims**:

[figure not shown]
- (1) Estimate the variability in CBF (measured by arterial spin labeling and perfusion MRI) and levels of putative biomarkers of the conditioning response (vasodilatory, inflammatory, fibrinolytic, microRNA) in the two treatment groups at enrollment and after 30 days of treatment.
- (2) Compare the changes in CBF and putative blood biomarkers of the conditioning response from enrollment to 30 days between the two treatment groups.
- (3) Obtain preliminary feasibility, tolerability and adherence data on the use of a RLIC device for secondary stroke prevention in subjects with ICAS.

This study will provide preliminary data to enable planning of a subsequent grant submission to NIH to perform a Phase I / II trial with the following goals: to provide more rigorous data on the mechanisms of action of RLIC, and to determine the potential efficacy of RLIC for preventing stroke in high-risk subjects with ICAS. Our ultimate goal is to perform a large randomized multicenter NIH-funded Phase III trial to determine the efficacy of RLIC for preventing stroke.

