### 3. OVERVIEW OF STUDY DESIGN

The design of the study is illustrated in Figure 1 below. In this prospective randomized pilot study, 10 eligible high-risk subjects with ICAS will be randomized to RLIC (bilateral upper extremity (BUE) daily for 30 days) plus AMM (n=5) or AMM alone (n=5). The AMM, which will be started at study enrollment and continued until close-out in all subjects, will consist of aspirin 325 mg per day, clopidogrel 75 mg per day, and risk factor management primarily targeting a systolic BP < 140 mmHg and LDL cholesterol < 70 mg /dl. All subjects will undergo baseline brain arterial spin labeling (ASL) and perfusion MRI to measure CBF and have blood drawn for biomarkers 3-5 days after randomization to allow for washout of any effect from the test RLIC treatment that will be done prior to randomization to determine the subjects' tolerability to RLIC treatment (see section 5 for more details on screening test). The period of 3-5 days will provide flexibility for scheduling these tests. After the baseline MRI and biomarker tests are completed, the subjects randomized to RLIC will begin daily RLIC for 30 days. Each daily BUE RLIC treatment will consist of 4 cycles of 5-minute inflations of both blood pressure cuffs simultaneously to a pressure of 200 mm Hg with 5 minutes of reperfusion between each inflation using the Doctormate device (see Figure 2). All subjects will return for their close-out visits 33-35 days after enrolling in the study and will undergo brain ASL and perfusion MRI and have blood drawn for biomarkers at that visit. The study will be conducted at 4 sites (MUSC, MCG, UCLA, USC) to enable us to evaluate the consistency of CBF measurements across multiple sites and to ensure that the recruitment target of 10 subjects will be met in time to allow for the subsequent NIH grant submission in 2017.

Figure 1. Overview of Study Design

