## **13. PROTECTION OF HUMAN SUBJECTS**

**Risks to the Subjects:** The risks of the Doctormate device might include discomfort, numbness or tingling in the hands and arms when the device is inflated, and a warm feeling when it is deflated. The device may also cause bruising in the arm or petechiae. There is also the theoretical possibility of a small risk of a venous clot

forming in the arm. However, in our review of the literature we have not found any reports of blood clot formation with RLIC and there were no instances of venous thrombosis or any serious adverse event in either of the two published trials in China. In one of those trials, 30 subjects over age 80 used the Doctormate device twice per day on both arms for 6 months and the following risks were noted in that trial: "Transient sporadic petechiae were observed in 3 cases during the first 30 days of the study, but disappeared soon after without discontinuing treatment. No ecchymosis, tenderness to palpation, edema, skin breakage, or other skin lesions were observed. No deep vein thromboses were detected by vascular sonography during or at the end of the 180 days of treatment". In our pilot trial, we will only be using the device once per day for a period of 30 days, which is a considerably lower dose than previously used in the two Chinese trials. In both animal and human experiments for cardiac or brain conditioning, there are no examples where RLIC increased CBF above normal levels or resulted in intracerebral hemorrhage.

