### **Protection Against Risk**

The research coordinator will call subjects randomized to the RLIC group weekly and will use a standardized questionnaire to ask subjects about adverse events (see Appendix 1). For the pain question, we will utilize a visual analog pain scale of 0 to 10 and provide this to the subjects randomized to the RLIC group. At the weekly phone call, the research coordinator will ask the degree of pain using this scale. If the score is > 2, the site investigator will be notified and will contact the subject by phone to review the level of discomfort. Additionally, If the subject answers "yes" to any other questions, we will ask the subject to come in to be examined. If we suspect a venous thrombosis because of swelling or pain, we will perform a venous ultrasound to rule out a deep venous thrombosis. We will also obtain the phone number of a relative or friend in order to reach the subject if we have trouble reaching the subject. All subjects will be given the telephone numbers of the principal site neurologist and site coordinator to report any clinical events or to ask questions about the study.

Subjects who are claustrophobic will not be enrolled in this study. To reduce the risk of phlebotomy, only trained phlebotomists will perform venipuncture. All neuroimaging and biomarker data will be de-identified as stated under "Sources of Material". Copies of the source documents used to collect data for study subjects will be kept in confidential binders at the participating sites. All these measures will ensure against loss of confidentiality.

Side effects of any medications prescribed to subjects as part of routine care of subjects with intracranial stenosis will also be monitored. These side effects will be minimized by recommending use of enteric-coated aspirin, checking liver enzymes and CK for subjects on a statin if clinically indicated, and instituting appropriate treatment should side effects arise.

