
Subject Study Number \_\_\_\_\_

End of Week (Circle one) 1.\_\_\_\_\_, 2.\_\_\_\_\_, 3.\_\_\_\_\_, 4. (close-out visit) \_\_\_\_\_

Date\_\_\_\_\_

1.) Have you experienced any swelling in either of your arms? (Y/N)

*Coordinator Comment: (if yes, specify which arm(s) and where in the arm(s), i.e., above, at or below cuff)*

2.) Have you had any discoloration (change in color) in either of your arms after any treatment? (Y/N)

This could be redness, blueness, small red dots, red or purple blotches in your arm

*Coordinator Comment: (if yes, specify which arm(s), where in the arm(s), and type of discoloration)*

3.) Have you had any persistent tingling or numbness in either of your arms? (Y/N)

*Coordinator Comment: (if yes, specify which arm(s) and where in the arm(s))*

4.) During the cuff inflations or any time between use of the cuff, have you had pain in either arm? (Y/N)

*Coordinator Comment: if yes, ask subject to use visual analog pain scale given to subject after enrollment to rate the discomfort on the Pain scale between 0 and 10, and specify which arm(s) and where in the arm(s) is the pain located) Pain rating\_\_\_\_\_*

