**Appendix 2.****Subject Diary**

Subject Study Number \_\_\_\_\_

Day	Completed? Y/N	Pain in an Arm? Y/N Grade (0-10) If yes, call coordinator	Arm discoloration, swelling, or tingling? (Bruising, etc). Y/N If yes, call coordinator	Specify type of problem or any other comments
1				
2				
3				
4				
5				
6				
7				
8				
9				
10				
11				
12				
13				
14				
15				
16				
17				
18				

19				
20				
21				
22				
23				
24				
25				
26				
27				
28				
29				
30				

Research Coordinator Name and Contact Number:

Principal Investigator Name and Contact Number:

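### Neither the weekly questionnaire nor the diary records whether arm pain came during cuff inflation or between sessions, so the only graded tolerability score mixes the two

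*Combined protocol and SAP*

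**What the plan says.** Section 2 makes tolerability part of the third primary aim: "Obtain preliminary feasibility, tolerability and adherence data on the use of a RLIC device". Section 3 randomizes subjects to RLIC "plus AMM (n=5) or AMM alone (n=5"), so five subjects use the device at home.

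Two forms collect their symptoms.

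- **Weekly questionnaire (Appendix 1).** Item 4 asks "During the cuff inflations or any time between use of the cuff, have you had pain in either arm? (Y/N"). If the answer is yes, the coordinator takes one rating from 0 to 10 and notes which arm and where. Swelling (item 1) and discoloration (item 2) have their own yes/no questions. So does the third symptom (item 3): "Have you had any persistent tingling or numbness in either of your arms".
- **Daily diary (Appendix 2).** One column takes pain as yes/no with a 0-10 grade. A second column takes "Arm discoloration, swelling, or tingling" under a single yes/no. Both tell the subject to call the coordinator if the answer is yes. A last column asks for the type of problem and any comments.

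Section 13 gives arm symptoms two meanings. Its risk text lists "discomfort, numbness or tingling in the hands and arms when the device is inflated" among the possible effects of the device. Under Protection Against Risk, the weekly pain score drives a contact rule ("If the score is > 2, the site investigator will be notified"), and pain is one of two cues for a venous ultrasound ("If we suspect a venous thrombosis because of swelling or pain").

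**The concern.** Pain while a cuff is inflated to 200 mm Hg and pain that is present hours later answer different questions. The first describes how bearable the treatment is. The second bears on tolerability too, but may also be an early sign of the arm problems listed in Section 13, such as venous thrombosis or muscle or nerve injury. A form that takes one rating for both leaves the reader of a recorded 4 unable to say which it was.

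This matters more here than on a routine adverse-event form. Section 13 says that the pilot will supply key tolerability data for the next trial. The pre-randomization test in Section 5 is a single 5-minute inflation, whereas the regimen in Section 3 is four 5-minute inflations daily for 30 days. These two forms are therefore the main symptom record under the full regimen. The 0-10 pain rating is their only graded item; everything else is yes/no or free text.

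The diary has a smaller problem of the same kind. Tingling, an expected sensation, shares a box with swelling, which is a cue for suspected thrombosis.

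**Working it through.** The plan states no figure for this point, so there is none to reproduce. The check is a comparison of the two forms, a count, and a short illustration.

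**1. What each form can separate in a structured field**

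| Distinction | Weekly questionnaire (Appendix 1) | Diary (Appendix 2) |
|---|---|---|
| Pain during inflation or between sessions | No: one yes/no and one rating | No: one yes/no and one grade |
| Pain or swelling | Yes: items 4 and 1 | Yes: separate columns |
| Swelling, discoloration or tingling | Yes: items 1, 2 and 3 | No: one yes/no, then free text |
| Scope of the tingling question | Persistent tingling or numbness | Any tingling; numbness not named |
| Worst or typical pain | Not stated | Not stated |

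Pain timing is the one distinction that neither form makes.

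**2. How many records are involved**

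Inputs: 5 RLIC subjects (Section 3), 4 weekly forms (Appendix 1, weeks 1 to 3 and close-out), 30 diary days (Appendix 2).

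- Weekly ratings: 5 × 4 = 20
- Diary grades: 5 × 30 = 150

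Both are maxima, because a rating is taken only when pain is reported.

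**3. What one score can hide (illustration)**

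The documents give no pain levels, so the values below are assumptions. Let I be a subject's usual inflation pain and B a new between-session pain.

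*If the subject reports the worst pain*, score = max(I, B), which stays at I whenever B ≤ I.

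| Assumed I | Values of B that leave the score unchanged | Score above 2 without any B? |
|---|---|---|
| 1 | 1 | No |
| 3 | 1 to 3 | Yes |
| 5 | 1 to 5 | Yes |

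Under this reading any B above 2 still gives a score above 2, so the notification is not missed. What is lost is the information in it: with I at 3 or 5 the rule is met every week, whether or not anything new has happened.

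*If the subject reports an average instead*, score = (I + B) / 2. With I = 5 and B = 1 the score is (5 + 1) / 2 = 3, lower than the usual 5 although a new pain has appeared. With I = 0 and B = 4 it is (0 + 4) / 2 = 2, which does not exceed 2. The forms do not say which reading applies.

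**4. Whether the analysis plan resolves it**

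Section 12 covers CBF, biomarkers and their correlation. It describes no summary of pain or other tolerability data, so nothing there separates the two settings.

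**The case against.** The strongest reply is that the forms prompt contact and are not the whole of safety monitoring. The weekly form asks about swelling, discoloration and persistent tingling separately. Any yes in either diary symptom column, at any pain grade, tells the subject to call the coordinator. A weekly score above 2 brings a phone review by the site investigator, a yes to any other weekly item brings an examination, and the ultrasound depends on clinical suspicion with no score cutoff. The Safety Officer judges whether an event is related to the device. With five treated subjects, each case can be read individually.

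Most of this stands. A reader might infer that tolerability cannot be separated at all from the arm-injury or thrombosis signal. The documents do not support that: swelling has its own weekly item, pain has its own diary column, and the follow-up steps give a clinician several chances to ask when the pain occurred. Nor is it right that the two forms count different things under one label. Their tingling wording differs openly, nothing says that the answers are pooled, and a broad daily prompt beside a narrower weekly question is a possible design.

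The reply does not cure the pain rating. Follow-up may recover timing as narrative, but no prompt on either form asks for it, and the separate weekly items say nothing about pain.

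**Conclusion.** The point holds for data capture. On both forms, up to 20 weekly ratings and 150 diary grades have no structured field for pain during inflation as against pain between sessions, and the diary depends on free text to tell tingling from swelling or discoloration. The graded tolerability result for aim 3 will therefore be hard to interpret. Timing that was not recorded cannot be reliably recovered afterwards.

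The effect is modest. Five subjects are treated, clinical follow-up is in place, and Section 12 plans no pain-score estimate that could be biased. No safety event is shown to be missed; the masking example rests on assumed pain levels and an assumed way of reporting them. The conclusion also assumes that the opening text of Section 6, which was not available for this check, adds no instruction to record pain timing. This is a cheap improvement, not a flaw that threatens the pilot.

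**What to change.** 1. In Appendix 1 item 4 and in the diary pain column, replace the single rating with two: worst pain during inflation and worst pain outside treatment. Report them separately.
2. In the diary, give discoloration, swelling, and tingling or numbness their own yes/no fields. Do not carry the word persistent over from the weekly form: Appendix 1 does not define it, and adding it would reduce the symptoms that prompt a call to the coordinator.
3. The sponsor should state which of the two ratings the pain-notification rule under Protection Against Risk refers to, and reconcile the tingling wording of the two forms. No threshold is proposed here.

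Cost: edits to two short forms and a few REDCap fields, one more question per weekly call, and a few more diary columns for the subject to fill in.

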**Appendix 2.****Subject Diary**

Subject Study Number \_\_\_\_\_

Day	Completed? Y/N	Pain in an Arm? Y/N Grade (0-10) If yes, call coordinator	Arm discoloration, swelling, or tingling? (Bruising, etc). Y/N If yes, call coordinator	Specify type of problem or any other comments
1				
2				
3				
4				
5				
6				
7				
8				
9				
10				
11				
12				
13				
14				
15				
16				
17				
18				

19				
20				
21				
22				
23				
24				
25				
26				
27				
28				
29				
30				

Research Coordinator Name and Contact Number:

Principal Investigator Name and Contact Number:
